8 STUDY ASSESSMENTS AND PROCEDURES

8.1 EFFICACY ASSESSMENTS

8.1.1 VISIT SCHEDULE OVERVIEW

The participant-related activities of the BESST trial can be divided into 4 phases:

- Screening for eligibility for enrollment (up to 3 visits over 8 weeks)
- Randomization to treatment (1 visit)
- Treatment phase (3 visits over 4 weeks: 1 visit at 2 weeks and 2 visits at 4-weeks)
- Post-treatment washout phase (1 visit at 6 weeks)

8.1.2 SCREENING AND BASELINE DATA COLLECTION

Patients that are likely to meet eligibility requirements after clinic visit or chart review of standard of care tests and procedures will be invited to undergo screening. The study will be explained to the potential participant, and if interested, the patient will sign the IRB-approved consent form.

To minimize in-person contact time between the participant and staff during the Covid-19 pandemic and as permitted by the site-specific IRBs or sIRB, participants will be offered a telephone or virtual review of the consent in place of the in-person review of the consent. Signature of the consent will take place in person at the study

visit and after confirmation that all of the participant's questions about the study have been answered. Recording of screening data on GpCRC BESST forms may not start until the participant has signed the consent statement. Screening and baseline data collection procedures will include questionnaires ([see 8.1.5](#)) (baseline medical history, HADS, SF-36v2, GSRS, PAGI-QOL, PHQ-15, PAGI-SYM, symptoms side effects), physical examination and ECG, measurement of fasting complete blood count (CBC), comprehensive metabolic panel (CMP), thyroid stimulating hormone (TSH) and HbA1c, a Gastric Emptying Scintigraphy (GES) test, an Electrogastrogram (EGG) with water load test (on a separate day), a pregnancy test (if female of child-bearing potential) and fasting blood collection for serum and plasma banking. Prior therapy for gastroparesis and concomitant medications will be reviewed as outlined in the inclusion and exclusion criteria. Patient charts will be reviewed for historical medical information and procedures. A diagnostic upper endoscopy or an upper GI radiographic series will be scheduled if the potential participant has not had this test within the past two years.

Once a potential participant has agreed and consented to participate in BESST, a Gastric Emptying Scintigraphy (GES) test will be scheduled. In addition, the preference is to schedule the Electrogastrogram (EGG) with water load test within a week of the GES test. Immediately prior to the GES test, females of childbearing potential must have a negative pregnancy test. For the GES test, the participant will arrive at the clinic after an 8-hour fast, that is nothing by mouth after midnight except for small sips of water and narcotic free the 3-days prior to the test. The PAGI-SYM questionnaire ([see section 8.1.5a](#)) will be completed and then the participant will undergo the GES test as described in [section 8.1.6](#). Symptoms will be monitored at the beginning and during the GES test.

The potential participant will be given a set of the daily symptom diary (ANMS GCSI-DD) forms to complete each night at home. These are returned to the clinic at their second clinic screening visit after 7-days have been completed.

For the second screening visit, the participant will arrive at the clinic after an 8-hour fast, that is nothing by mouth after midnight, and have the EGG with water load test as described in [section 8.1.6](#).

The GpCRC BESST web-based database management system has an application to check patient eligibility based on data forms keyed and verified into the study database. The eligibility check application is used during screening a patient to show failed inclusion/exclusion eligibility checks, to show missing required data. Clinic staff can use this task to identify the items that still need to be completed, keyed, or verified after data from the screening visits are keyed. To avoid inconvenience to potential participants, the randomization application should not be attempted until the eligibility check application indicates that the patient is eligible except for the items that can only be completed at the randomization visit.

8.1.3 RANDOMIZATION VISIT

The randomization visit is the visit at which randomization takes place and the participant is issued the study medication which is randomly assigned to the participant. Randomization is the act of generating the random study medication assignment and is the procedure which defines a participant's enrollment into the trial. Randomization can occur after eligibility has been fully checked and all data collected at the screening visits have been keyed to the trial database. Since these processes take time, randomization cannot be done at a screening visit, and since study medication needs to be issued to the participant, the randomization visit must be completed in person with the participant. Therefore, a visit separate from the screening visits is necessary. Since this will be a visit on a different calendar day and medication will be started at this visit, good clinical practice requires that a few basic checks of the participant's well-being be completed at the randomization visit.

The procedures completed at the randomization visit are: pregnancy test for females of child bearing potential, verification that the participant is feeling well, affirmation of consent, review of concomitant drugs and vital signs (systolic and diastolic blood pressure, heart rate, respiratory rate, body temperature). All participants will be given information on a healthy life style and gastroparesis diet, and instructions on when to take their drug, and information to be aware of while taking buspirone (see section [6.1.2](#)). A set of daily-dairy forms will be distributed to the participant to complete each day and return to the clinic at their week 2 study visit.

8.1.4 FOLLOW-UP VISITS

Participants will return to the clinical center for follow-up visits at 2 and 4 weeks. A post-treatment washout phase visit will occur at week 6. Each visit will have an interval of time surrounding the ideal date for the visit during which the visit may be done and the data included in the trial database. The ideal date for the week 2 visit is the randomization date plus 2 weeks (14 days); the ideal date for the week 4 visit is the randomization date plus 4 weeks (28 days). Visit windows will be constructed to be contiguous, so that at any point in time, some visit window is open, subject to a check on the minimum separation of at least one week between consecutive visits. The specific assessments and procedures required at each of the follow-up visits are:

- **Week 2:** pregnancy test for females of child bearing potential, follow-up medical history with review of adverse events, concomitant medications and study adherence, assessment of vital signs (systolic and diastolic blood pressure, heart rate, respiratory rate, body temperature), and the following surveys: Hospital anxiety and depression (HADS), PAGI-SYM, and the Clinical Patient Grading Assessment Scale (CPGAS)([see section 8.1.5](#)) and a symptoms side-effect questionnaire (see [section 8.2](#) for details). In addition, the participant will return their Daily-Diary forms and receive another set to complete for return at the Week 4 visit.
- **Week 4:** the week 4 visit will require two fasting visits scheduled as close together as possible, preferably 1 day apart.
 - The participant will refrain from taking their buspirone the morning of the GES test, and take it 30 minutes prior to the GES test. Information to be collected at this visit includes: pregnancy test for females of child-bearing potential, a GES test, follow-up medical history with review of adverse events and concomitant medications, physical exam and ECG, fasting blood draw for CMP and CBC, review of adherence and the following surveys: HADS, SF-36v2 Quality of Life, PAGI-SYM, GSRS, PAGI-QOL, PHQ-15, symptom side-effects, and the CPGAS. Fasting blood will be drawn for serum and plasma banking. In addition, the participant will return their daily-diary forms and receive one more set of daily-diary forms to complete each night to return at their 6-week visit.
 - The EGG test with water load test will be undergone the morning of the following day or as soon as can be possibly scheduled within the visit window. The participant will wait and take their buspirone dose 15 minutes prior to the EGG baseline recording. The participant will return all bottles of the study drug dispensed to the clinic staff. The participant will be instructed to not take any more drug after this visit.
- **Week 6:** At this visit, the participant will return their final set of daily-diary forms. Information to be collected includes: the follow-up medical history form with review of adverse events and concomitant medications, physical exam and fasting blood draw for CMP, CBC, and for banking plasma and serum with the NIDDK Biorepository, and the following questionnaires: HADS, PAGI-SYM, GSRS, PAGI-QOL, symptom side-effects, CPGAS. A BESST study close-out form will document the participant's end of participation in BESST.

8.1.5 STANDARDIZED QUESTIONNAIRES

Standardized questionnaires to assess efficacy:

Several standardized questionnaires will be administered to participants enrolled in the BESST trial. Questionnaires will be administered at baseline (prior to randomization) and during follow-up at specified intervals (see [1.3](#) for the Schedule of Activities). The purpose of the questionnaires is to obtain information regarding gastroparesis symptoms, side effects, and health-related quality of life.

- a. **The Patient Assessment of Upper GI Symptoms (PAGI-SYM)** assesses the severity of symptoms of gastroparesis, functional dyspepsia, and gastroesophageal reflux disease [24]. The scale assesses symptoms over the prior two weeks, graded by the participant from none (0) to very severe (5). It includes the nine symptoms of the Gastroparesis Cardinal Symptom Index (GCSI), a validated patient-reported outcome (PRO) for gastroparesis using a two-week recall period. The nine symptom GCSI (nausea, vomiting, retching, stomach fullness, unable to finish a meal, feeling excessively full after meals, loss of appetite, bloating, belly visibly larger) is based on three subscales (postprandial fullness/early satiety, nausea/vomiting, and bloating) [25]. The PAGI-SYM also includes upper abdominal pain, which will be used for this study. The PAGI-SYM is in the public domain for use by investigators and physicians.
- b. **ANMS GCSI-DD** is a daily dairy developed by the American Neurogastroenterology and Motility Society (ANMS) for gastroparesis [26]. The ANMS GCSI-DD is undergoing qualification by the FDA for use as a patient-reported outcome (PRO) outcome for clinical trials evaluating new treatments for either diabetic or idiopathic gastroparesis [27]. The ANMS GCSI-DD consists of five core symptoms (nausea, vomiting, early satiety, postprandial fullness, upper abdominal pain). Each night, participants grade the severity of symptoms over the prior 24 hours. The ANMS GCSI-DD core symptom composite score (an average of the five core symptoms) is designed to detect clinical improvement in symptoms of gastroparesis and to be used as a PRO outcome for clinical trials.
- c. **Clinical Patient Grading Assessment Scale (CPGAS)** will be used to help assess the therapeutic response of the participants. Participants will be asked if their rating of relief of symptoms during the past week compared to the way the participant usually feels has improved, stayed the same, or worsened with study treatment. The clinical response of their gastroparesis symptoms to study treatment with one point gradations from (+7) = completely better; (0) = no change, and (-7) = very considerably worse. Responders are defined as those with score of > 0 and non-responders with score of ≤ 0 by CPGAS [28].
- d. **Health Survey (SF-36v2)** is a 36-item, self-report measure designed to assess quality of life in participants [29]. This measure also provides two summary scores (physical and mental health) and eight scale scores. It is reliable and internally consistent. A higher summary score indicates better quality of life.
- e. **Patient Assessment of Upper Gastrointestinal Disorders-Quality of Life (PAGI-QOL)** is a self-completed disease-specific quality of life questionnaire; the respondent scores each of 30 factors from 0 (none of the time) to 5 (all of the time) [30]. Items cover how often gastrointestinal problems have affected different aspects of their quality of life and well-being in the past two weeks. There are five domains: Daily Activities, Clothing, Diet and Food Habits, Relationship, and Psychological Well-Being and Distress. Overall PAGI-QOL scores are calculated by taking means of all subscores after reversing item scores; thus a mean PAGI-QOL score of 0 represents poor quality of life while 5 reflects the best life quality.
- h. **The Hospital Anxiety and Depression Scale (HADS)** [31] was developed by Zigmond and Snaith (1983) and is commonly used to determine the levels of anxiety and depression that a patient is experiencing. The HADS is a fourteen-item scale that generates ordinal data. The HADS is comprised of 2 subscores, each scored from 0-21 points: HADS-A is the anxiety subscore and HADS-D is the depression subscore. Each subscore includes 7 questions which are each scored from 0 (not at all) to 3 (most of the time). The items for each subscore are summed and the average results in the subscore.

g. The **Gastrointestinal Symptoms Rating Scale (GSRS)** is a clinical rating scale for gastrointestinal symptoms in participants with irritable bowel syndrome and peptic ulcer disease [32]. There are 15 items on the instrument, which are scored on a 7-point Likert scale from 0=no discomfort to 7=very severe. Using the scoring manual, total score and 5 scales can be computed (Abdominal pain, Reflux syndrome, Diarrhea syndrome, Indigestion syndrome, Constipation syndrome).

h. The **Patient Health Questionnaire 15 Somatic Symptom Severity Scale (PHQ-15)** [33] is a brief, self-administered questionnaire that may be useful in screening for somatization and in monitoring somatic symptom severity in clinical practice and research. The total PHQ-15 score ranges from 0 to 30 comprising the sum of 15 somatic symptoms in the past 4 weeks rated in severity from 0 (not bothered at all) to 2 (bothered a lot).

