1. Gastroparesis Cardinal Symptom Index (GCSI) total score;
GCSI is comprised of the first 9-items of the PAGI-SYM questionnaire.
2. Four PAGI-SYM questionnaire subscores: nausea/vomiting (3 items: nausea, retching, vomiting), bloating (2 items: bloating, stomach visibly larger), upper abdominal pain (2 items: upper abdominal pain, upper abdominal discomfort), GERD (7 items: heartburn during the day, heartburn when lying down, feeling of discomfort inside chest during the day, feeling of discomfort inside chest during sleep, regurgitation or reflux during the day, regurgitation when lying down, bitter, acid or sour taste in mouth)
3. Eight single-item PAGI-SYM questionnaire symptom severity scores: nausea, vomiting, stomach fullness, inability to finish a normal-sized meal, feeling excessively full after meals, loss of appetite, bloating, upper abdominal pain
4. Gastrointestinal Symptom Rating Scale (GSRS) total score
5. Clinical Patient Grading Assessment Scale (CPGAS) score
6. Patient Assessment of Upper Gastrointestinal Disorders-Quality of Life (PAGI-QOL) questionnaire total score
7. Hospital Anxiety and Depression Scale (HADS) questionnaire anxiety score and depression score
8. Patient Health Questionnaire 15 Somatic Symptom Severity Scale (PHQ-15) questionnaire total somatization score
9. SF-36v2 Quality of Life questionnaire Physical Component Score and Mental Component Score
10. Percent gastric emptying retention at 2 and 4-hours.
11. Anthropometric measurements (Body Mass Index (BMI)/ weight, waist circumference) (safety)
12. ECG measures (safety)
13. Laboratory measures (ALT, creatinine, glucose) (safety)
14. Frequency of side effects and adverse events, as well as severity of adverse events. (safety and tolerability)

Exploratory/Ancillary Outcomes: These outcomes either use novel techniques (items 1, 2, and 3) or are outcomes that have lower statistical power yet might provide insight into paths for future research (items 4,5). The outcome measures are changes over 4 weeks (week 4 minus baseline) in:

1. Intragastric meal distribution (IMD) as a measure of Fundic Accommodation (FA) using digital analyses of the GES test images
2. Gastric dysrhythmia and volume of water consumed until full measured with electrogastrogram (EGG) with water load satiety test

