8.2 SAFETY AND OTHER ASSESSMENTS

Assessments for Safety

- **Physical examination** (e.g., height, weight, waist measurements, vital signs (temperature, heart rate, respiratory rate, blood pressure, ECG).
- **Laboratory results** – All labs including creatinine, ALT, and glucose will be monitored at sites and in the central database and all abnormal values will be managed by the site investigator. If the ALT, creatinine, or glucose levels are elevated, that measure will be repeated within 5 days. If necessary, the participant will be given management advice and information will be provided to the participant's PCP.
- **Standardized Questionnaires:**
 - a. **Symptom side effects:** Participants will be asked if they experienced any side effects from the BESST drug treatment and to describe any side effects. The baseline and follow-up medical histories will inquire about symptoms that may be attributed as side effects of buspirone using a standard set of questions. These symptoms include: headache, dizziness, tiredness, drowsiness, sleep problems (insomnia), nausea, upset stomach, blurred vision, nervousness or excitement.
 - b. **Adverse Event Report form:** This form will document occurrence of an adverse event that threatens the integrity of the BESST trial or the well-being of a study participant during the trial.
 - c. **Serious Adverse Event/IND Safety Report:** This form will document occurrence of any event reported on the Adverse Event Report form that satisfies the FDA expedited IND Safety Report requirement.

- **Biological specimen collection and laboratory evaluations are included in the Schedule of Activities and section in 12.2.** Instructions for the preparation, handling, storage, and shipment of specimens are detailed in the BESST Standard Operating Procedures manual.

If a participant has scores on the psychological questionnaire indicating significant anxiety or depression (HADS-A ≥ 15 and/or HADS-D ≥ 15 indicating severe symptoms) or by the clinician's assessment, the clinical center investigator or staff will suggest that they see a clinical psychologist or psychiatrist and information on these referrals will be given to the participant [37]. If the clinician is concerned that a participant is actively suicidal or at risk of self-harm, the clinical center investigator will help make arrangements for them to be seen that day for further assessment.

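### The HADS scoring sentence ends in an average (maximum 3), while the stated range of 0-21, the threshold of 15 and the named outcomes all require the sum

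*Combined protocol and SAP*

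**What the plan says.** The HADS paragraph in section 8.1.5 describes 14 items in two subscores of seven, with each item scored 0 to 3. It gives the range first: "The HADS is comprised of 2 subscores, each scored from 0-21 points". It closes with the scoring rule: "The items for each subscore are summed and the average results in the subscore". No other sentence in the document says how HADS items become a subscore.

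Three other places depend on that score:

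- **Section 8.2** sets a criterion for suggesting mental-health follow-up, "HADS-A ≥ 15 and/or HADS-D ≥ 15 indicating severe symptoms". The same sentence gives a second route that does not use the score: "or by the clinician's assessment, the clinical center investigator or staff will suggest that they see a clinical psychologist or psychiatrist". The questionnaire paragraph in section 2.3.1 tells the reader that participants with significant HADS scores will be referred, and points to section 8.2.
- **Section 1.1** lists as a secondary outcome the change in "Hospital Anxiety and Depression Scale (HADS) questionnaire anxiety score and depression score", and section 3 repeats it. Section 9.1 describes the same two outcomes as HADS totals.
- **Section 9.4.3** analyses continuous secondary outcomes by ANCOVA of the 4-week change on treatment group and baseline value, with nominal p-values.

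The schedule in section 1.3 collects HADS at screening and at weeks 2, 4 and 6.

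**The concern.** A range of 0-21 and an averaged subscore cannot both be right for seven items scored 0 to 3. The sentence that conflicts with the rest is the only explicit scoring instruction for this instrument, and it stands in the assessment section that a programmer or coordinator would consult.

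An averaged score would not look odd in this protocol. The primary PAGI-SYM subscore is an item average, the daily-diary composite is an average, and the PAGI-QOL paragraph just above HADS uses means. Someone scoring HADS from section 8.1.5 could follow the last sentence without noticing the conflict.

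Two things depend on the reading: whether the section 8.2 criterion can be met on the score at all, and the scale on which two secondary outcomes are reported.

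**Working it through.** **Inputs.** Items per subscore: 7. Item range: 0 to 3. Stated subscore range: 0 to 21 (all from section 8.1.5). Threshold: 15 on either subscore (section 8.2). Model: ANCOVA of change on group and baseline (section 9.4.3).

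**Step 1: reproduce the stated range.** Sum of the items: minimum 7 × 0 = 0, maximum 7 × 3 = 21. This is the protocol's 0-21 exactly.

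**Step 2: apply the scoring sentence as written.** Average of the items: minimum 0/7 = 0, maximum 21/7 = 3. The stated range is not reproduced.

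**Step 3: compare with the threshold.** On the sum scale, 15 lies within 0-21 and can be reached. On the average scale the maximum is 3, which is below 15, so the score-based criterion cannot be met at any of the four scheduled assessments. (A sum of 15 corresponds to an average of 15/7 = 2.14. This is given only to show the distance between the scales, not as an alternative threshold.)

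**Step 4: effect on the analysis.** Let Y be the week-4 sum and B the baseline sum. The planned model is Y − B = a + d·(group) + c·B + error. Dividing every score by 7 gives (Y − B)/7 = a/7 + (d/7)·(group) + c·(B/7) + error/7. The treatment difference, its standard error and its confidence limits are all divided by 7. Their ratio, and so the p-value, is unchanged.

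A simulated data set of 108 participants, 54 per group, shows this. Its values are invented and say nothing about the effect to expect.

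| Scale | Adjusted difference | 95% CI | p |
|---|---|---|---|
| Sum (0-21) | −1.355 | −2.353 to −0.356 | 0.0083 |
| Average (0-3) | −0.194 | −0.336 to −0.051 | 0.0083 |

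Check: −1.355/7 = −0.194.

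**Step 5: the limit of step 4.** The factor of 7 is constant only if all seven items are answered. If six items are answered, each at 3, the plain sum is 18 and the average of the answered items is 3, a ratio of 6. The invariance of the p-value is therefore claimed for complete data only.

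**Step 6: check the neighbouring instrument.** Section 8.1.5 describes PHQ-15 as a sum of 15 items scored 0 to 2, with range 0 to 30, and 15 × 2 = 30. There the rule and the range agree, so the mismatch is specific to the HADS sentence.

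**The case against.** The strongest reply is that the document already settles the question. The 0-21 range stands in the same paragraph, the threshold of 15 makes sense only for a sum, section 9.1 speaks of totals, and even the faulty sentence says first that the items are summed. HADS is a cited standard instrument, and nothing in section 9 adopts averaging for it. A careful reader would take the last clause as a slip. This stands: it shows which reading is intended and keeps the point minor. It does not remove the contradiction, because no passage withdraws the clause.

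A reader might also draw stronger conclusions, which the documents do not support:

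- **That the data system would fail to flag distressed participants.** No automated HADS flag is described. Section 8.2 gives the action to the investigator or staff. The data-system checks that are described concern eligibility and range, logic and consistency edits. How HADS was actually coded cannot be seen from the documents.
- **That nobody could be referred.** Only the score-based route would be closed. The clinician's assessment remains, as does the separate same-day pathway in section 8.2 where suicidality or self-harm is a concern.
- **That dividing by 7 loses effect or power.** It is a change of units. With complete data the test is identical.

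**Conclusion.** The contradiction is real and confined to one clause. Read literally, it caps each subscore at 3 against a stated maximum of 21 and a threshold of 15. The score-based criterion in section 8.2 then becomes unreachable, and the adjusted differences and confidence limits for two secondary outcomes shrink to one-seventh of the stated scale. They could not then be read against the protocol's own range or its severity cut-off.

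The p-values with complete data, the primary outcome and the sample size of 108 do not change. The documents do not show that averaging was ever implemented, so they give no ground for saying that participant safety or the trial's conclusions are compromised.

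The conclusion rests on the item count and item range given in section 8.1.5. The size of the consequences depends on the sentence being followed literally, which the rest of the document makes unlikely. This is a minor wording correction.

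**What to change.** In the last sentence of the HADS paragraph in section 8.1.5, delete everything after the word summed, so that each subscore is the sum of its seven items with range 0-21. This brings the sentence into line with the range in the same paragraph, with section 8.2 and with section 9.1. The threshold and the referral procedure are not altered.

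Then confirm that the scoring used in the database and at the sites is on the 0-21 scale. The cost is one deleted clause and one scoring check. Design, sample size and analysis model stay as they are.
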